## Objective

This study examines static/dynamic balance performance, daily activities, and confidence in less fear of falling for people with Parkinson's disease (PD) performing in-home balance exercises with a smartphone-based wearable telerehabilitation system (intervention group). Twenty-two subjects with idiopathic PD will be potentially recruited.

## Study Design

The experimental design will include laboratory assessments (i.e., pre-assessment baseline at the beginning of week 1, post-assessment at the end of week 6, and retention-assessment 1 month after week 6) and in-home balance exercises. Participants will perform in-home balance exercises (3 days per week for 6 consecutive weeks) with the Smarter Balance System (SBS).

Laboratory assessments: Subjects will be quantitatively assessed for static/dynamic balance performance using a measure for the range of limits of stability (LOS) in both anterior-posterior (A/P) and medial-lateral (M/L) directions. After completion of the pre-assessment, a member of the research team will train all participants to use the SBS's smartphone, and all participants will be additionally trained in the use of the custom belt and the walker and multimodal biofeedback for in-home dynamic weight-shifting balance exercises (WSBE) guided by the SBS. After completion of the post-assessment, all participants will complete a usability and acceptability questionnaire (UAQ) for the SBS.

In-home balance exercises: All participants will use the SBSs for 6 consecutive weeks, and they will complete in-home WSBE (i.e., physical therapists' recommended dynamic balance exercises) with the SBS (3 days per week) in both A/P and M/L directions. All participants will perform in-home dynamic WSBE by standing inside a walker (no wheels). The instructional video provided by the SBS will show how to perform dynamic WSBE in both A/P and M/L directions by standing inside the walker without touching or holding onto it unless the subject experiences loss of balance. After each trial, the SBS's smartphone app will store exercise-related data.

Performance metrics: Measured data from the SBSs will be analyzed using MATLAB (The MathWorks, USA). Statistical analysis will be performed using SPSS (IBM Corp., Armonk, NY, USA). As a function of the pre/post/retention-assessments, two primary outcome measures (range of LOS) will be used to evaluate static/dynamic balance performance. Ranges of LOS in degrees correspond to the furthest deviations of the body tilt in both A/P and M/L directions. The UAQ score (Likert scale) will be used to assess the usability and acceptability of the SBS, and the participants' compliance with the in-home balance training regimens, total exercise time, and number of completed exercises will be quantitatively analyzed.

Name	Time Frame	Brief Description
Range of limits of stability	Pre-assessment (baseline at the beginning of week 1), post-assessment (at the end of week 6), and retention-assessment (1 month after week 6)	Limit of stability refers to the outermost range in anterior-posterior and medial-lateral directions at which the subject can lean from the vertical without changing the base of support.
Usability and acceptability questionnaire (UAQ)	Post-assessment (at the end of week 6)	The UAQ is a self-reported questionnaire used by subjects to assess the usability and acceptability of the proposed SBS.

## Statistical Analysis Plan

The primary outcome measure for evaluating balance performance is the range of Limits of Stability (LOS) in both the anterior-posterior (A/P) and medial-lateral (M/L) directions. LOS represents the maximum angular excursion that a participant can achieve while maintaining a stable base of support without stepping or losing balance. LOS will be measured at three time points: baseline (Week 1, prior to intervention), post-intervention (Week 6), and retention (Week 10, one month after the intervention ends). These measurements will be obtained using the SBS smartphone application, which quantifies participants' dynamic balance capacity by analyzing trunk sway and range of controlled movement.

To assess the efficacy of the SBS-guided intervention, Repeated Measures Analysis of Variance (ANOVA) will be used with time (baseline, post, retention) as a within-subject factor and group (intervention vs. control) as a between-subjects factor. Main effects of time and group, as well as the interaction effect (time  $\times$  group), will be evaluated to determine whether balance performance improved differentially over time depending on the assigned intervention. A significant interaction effect would suggest that the SBS system had a unique impact on improving LOS relative to the paper-based control regimen.

As a measure of user experience and technology acceptance, the Usability and Acceptability Questionnaire (UAQ) will be administered at the post-assessment time point (end of Week 6). The UAQ consists of self-reported Likert-scale items that evaluate perceived ease of use, clarity of instructions, comfort of the wearable system, motivation to exercise, and willingness to continue using the SBS. Responses will be summarized using descriptive statistics (mean, standard deviation) for each item. Between-group differences in total UAQ scores will be analyzed using independent samples t-tests to determine whether the intervention group rated the SBS as more usable and acceptable than the paper-based regimen.

All analyses will be conducted using IBM SPSS Statistics v29 (IBM Corp., Armonk, NY, USA), with the significance level set at  $\alpha = 0.05$ .

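### The sole LOS efficacy analysis, classical repeated-measures ANOVA, excludes anyone who misses a follow-up visit and has no stated sphericity correction; a mixed model with a named week-6 contrast should replace it

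*Combined protocol and SAP*

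**What the plan says.** The Objective gives the sample size without power, effect size or attrition allowance: "Twenty-two subjects with idiopathic PD will be potentially recruited". Study Design sets the two follow-up assessments: "post-assessment at the end of week 6, and retention-assessment 1 month after week 6".

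The Statistical Analysis Plan repeats the schedule ("LOS will be measured at three time points") and names one efficacy analysis for LOS: "Repeated Measures Analysis of Variance (ANOVA) will be used with time (baseline, post, retention) as a within-subject factor", with "group (intervention vs. control) as a between-subjects factor". The inference rests on the time-by-group term: "A significant interaction effect would suggest that the SBS system had a unique impact on improving LOS". Software and alpha are fixed ("All analyses will be conducted using IBM SPSS Statistics v29", "with the significance level set at" 0.05).

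No section covers missed assessments, the analysis population, imputation, a covariance structure, a sphericity test or an epsilon correction. The SPSS procedure is not named, nor is it stated which of the available F tests decides the result.

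**The concern.** Two properties of the named method matter here.

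- **Complete cases.** Classical repeated-measures ANOVA works on the full set of three values per person. Missing retention removes a participant from every time comparison, including baseline to week 6, where that person's data were collected. With 22 people planned, each loss is expensive. If retention attendance depends on week-6 performance, the people left are also a selected group.
- **Sphericity.** The uncorrected univariate F assumes that all pairwise differences between visits have equal variance. Here one visit precedes training and two follow it, and the gaps are unequal (six weeks, then about one month), so the assumption cannot be taken for granted. If it fails and the uncorrected F is used, the nominal 5% test rejects too often.

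At stake are the precision of the primary outcome, the direction of its error if attendance is selective, and the freedom to choose among F tests after seeing the data.

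**Working it through.** The plan has no power or attrition figure to reproduce. From the documents: N = 22, three occasions, alpha 0.05. Assumed, because the documents give nothing: missingness, within-person correlations and, for the two-group reading, 11 vs 11.

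**1. Precision.** With a share m missing independently at each follow-up, completers = 22(1−m)² and the standard error is multiplied by 1/(1−m). People seen at week 6 but dropped = 22[(1−m) − (1−m)²].

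| m per visit | Complete of 22 | SE rises by | Seen at week 6 but dropped |
|---|---|---|---|
| 5% | 19.9 | 5% | 1.0 |
| 10% | 17.8 | 11% | 2.0 |
| 15% | 15.9 | 18% | 2.8 |
| 20% | 14.1 | 25% | 3.5 |

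At m = 10%, about 18 are complete, and √(22/18) = 1.106. The effect detectable at 80% power (noncentral t, two-sided 0.05) is:

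- single arm, one-sample test of change: 0.626 SD at n = 22 and 0.701 SD at n = 18;
- two arms, difference in change: 1.26 SD of change at 11 vs 11 and 1.41 at 9 vs 9.

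**2. Bias.** All scenarios are illustrative.

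- *Single arm.* Baseline–week-6 correlation 0.7, true change zero, 19% dropout that is likelier with poor observed change. The completers' mean change is +0.145 outcome SD. The SD of change is √(2 × 0.3) = 0.775, so this is 0.145/0.775 = +0.19 SD of change.
- *Two arms, retention loss related to the week-6 value only in the intervention arm.* Correlations 0.6/0.5/0.7, true week-6 difference 0.5 SD. Complete-case bias at week 6 is +0.03 to +0.06 SD at 10% loss, +0.06 to +0.10 at 20% and +0.10 to +0.14 at 30%. At week 10 it is 0.00 to 0.03.
- *Two arms, same mechanism in both, about 20% dropout.* Bias in the group difference is about 0 when there is no effect, and about −0.07 SD when the true difference is 0.5 SD.
- *Missing completely at random.* No bias.

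In the second scenario, a likelihood analysis of all observed visits has bias within 0.01 SD. At 10/20/30% loss it holds the week-6 standard error at about 0.38 SD, against about 0.40/0.43/0.46 for complete cases. The week-10 gain is smaller: 0.44/0.46/0.50 against 0.45/0.48/0.52.

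**3. Error rate.** Epsilon = tr(A)²/[2 tr(A²)], where A is the covariance of the two orthonormal visit contrasts. Take correlations of 0.5 between baseline and each follow-up, and 0.9 between the follow-ups. The contrast variances are then 1 − 0.9 = 0.1 and (6 − 4 + 1.8)/6 = 0.633, with zero covariance. So epsilon = 0.733²/[2(0.01 + 0.401)] = 0.654. Simulated size of the 5% time-by-group test (11 vs 11, 100,000 trials each):

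| Epsilon | Uncorrected | Greenhouse-Geisser |
|---|---|---|
| 1.0 | 5.0% | 4.5% |
| 0.875 | 5.5% | 4.6% |
| 0.80 | 6.0% | 4.8% |
| 0.654 | 7.1% | 5.0% |
| 0.53 (near the floor of 0.5) | 8.3% | 5.0% |

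A single-arm time effect with n = 22 behaves almost identically.

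**4. Check on the remedy.** With complete data and an unstructured covariance, the two-df Wald F equals T²/2, and T²(ν−1)/(2ν) follows F(2, ν−1). Satterthwaite refers it to F(2, ν). For ν = 20 the critical value is 3.49, and P[F(2,19) > 3.49 × 19/20] = 5.8%; for ν = 21 it is also 5.8%. A one-df contrast does not have this problem.

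**The case against.** The strongest reply is that every harm is conditional. Nothing is lost if all 22 attend all visits. Bias also needs missingness related to outcome. The error rate moves only if sphericity fails and the uncorrected F is read, and the plan does not say which F will be used. A one-line Greenhouse-Geisser statement would settle that part. A mixed model has its own costs: it assumes missing at random, recovers little from people who miss both follow-ups, and with Satterthwaite df its omnibus test is mildly liberal at this size.

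All of that stands, and it rules out some stronger readings that a reader might infer:

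- *That the plan will overstate benefit.* This holds for a single-arm mean change, or where selective loss is confined to the intervention arm. For the time-by-group contrast with similar dropout in both arms, bias can be near zero or go either way.
- *That the error rate is seriously distorted, or distorted because N is 22.* The inflation comes from non-sphericity. It is modest under mild departures, and no document figure supports the strong pattern.
- *That one detectable-effect figure describes the trial.* The Objective and Study Design describe only users of the device, while the Statistical Analysis Plan adds a control group. Both sizes are therefore given; that conflict is a separate matter.

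The reply does not remove the complete-case rule. As written, it discards observed week-6 data from anyone who misses retention, and Greenhouse-Geisser does nothing about that.

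**Conclusion.** The point holds in conditional form and should be fixed before data are analysed. The omission is certain from the text; its size is not, because dropout, correlations and allocation are all assumed. Under 5–20% missing per follow-up, the cost is a 5–25% rise in standard errors. Bias is possible only under selective attendance, and its sign depends on the design and on which arm loses people. Type I error is about 5.3–5.8% under mild departures from sphericity (epsilon roughly 0.85–0.94), about 6% at 0.80 and 7–8% under strong departures, and only if the uncorrected F decides. These conclusions apply whether the trial has one arm (time effect) or two (interaction).

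**What to change.** Amend the Statistical Analysis Plan as follows, for A/P and M/L LOS alike:

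- Primary analysis: a linear mixed model (SPSS MIXED) using every observed LOS value from all enrolled participants. Use categorical visit, unstructured within-person covariance and REML. Add group and group-by-visit if a control arm exists.
- Deciding test: the one-df baseline-to-week-6 contrast (group difference in change if two arms) with a 95% CI. Retention is the second contrast.
- If an omnibus two-df test is kept, use a small-sample adjustment such as Kenward-Roger instead of Satterthwaite df alone.
- Sensitivity analysis: the complete-case ANOVA with Greenhouse-Geisser correction.
- State the missing-at-random assumption, and report how many people miss each visit.

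The cost is SAP wording and another procedure in the software already chosen. It needs no extra data, visits or participants.

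### The SAP's group comparisons need a paper-based control arm that the Objective and Study Design do not describe; the sections must be reconciled before analysis.

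*Combined protocol and SAP*

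**What the plan says.** The Objective describes people with Parkinson's disease "performing in-home balance exercises with a smartphone-based wearable telerehabilitation system (intervention group") and gives one number: "Twenty-two subjects with idiopathic PD will be potentially recruited". No second group is named there and the 22 are not divided.

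The Study Design section gives everyone the same programme:

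- Training: "a member of the research team will train all participants to use the SBS's smartphone".
- Home exercise: "All participants will use the SBSs for 6 consecutive weeks".
- Questionnaire: "all participants will complete a usability and acceptability questionnaire (UAQ) for the SBS".

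The outcome table in that section lists LOS range and the UAQ, and describes the UAQ as a rating of the SBS. Neither the section nor its table mentions a control arm, a paper-based regimen or a method of allocation.

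The Statistical Analysis Plan specifies a repeated-measures ANOVA "with time (baseline, post, retention) as a within-subject factor" and "group (intervention vs. control) as a between-subjects factor". It evaluates time, group and their interaction, and says how the interaction is to be read: "A significant interaction effect would suggest that the SBS system had a unique impact on improving LOS relative to the paper-based control regimen". It also plans an independent-samples t-test on total UAQ score, to see whether the SBS is rated above the paper-based regimen.

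**The concern.** The SAP analyses a two-group trial; the sections before it describe participants who all receive the same thing. The mismatch goes beyond loose wording, because the SAP relies on the comparator in the group factor, in the reading of the interaction and in the UAQ test.

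The comparative claim is at stake. The SAP's statement that the SBS improves LOS beyond a paper-based regimen rests on the interaction. If there is only one group, that term does not exist and the analyst must change the primary analysis, possibly once the data are in hand. The efficacy wording could then end up attached to an uncontrolled change over time. If there are two groups, the design text does not say who is in the second one, how they got there, how many there are or what they do at home.

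**Working it through.** The documents give no effect size, SD, power, allocation ratio or dropout, so there is no stated figure to reproduce. The check is whether the planned terms can be estimated.

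**Inputs.** Time has m = 3 levels and group has g = 2 levels (Statistical Analysis Plan). N = 22 (Objective). All participants use the SBS (Study Design). Alpha is 0.05 (Statistical Analysis Plan); two-sided is assumed for t-tests, since sidedness is not stated.

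**Step 1: rank of the model.** The group by time model has 2 × 3 = 6 mean parameters. With 22 participants at 3 visits, all in the SBS group, the design matrix has rank 3, so only the three visit means can be estimated. With two groups (11 and 11 assumed) the rank is 6.

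**Step 2: degrees of freedom**, assuming all 22 are complete.

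| Term | Formula | One group (g = 1) | Two groups (g = 2) |
|---|---|---|---|
| Group | g − 1 | 0 | 1 |
| Time × group | (g − 1)(m − 1) | 0 | 2 |
| Time | m − 1 | 2 | 2 |
| Within-subject error | (N − g)(m − 1) | 21 × 2 = 42 | 20 × 2 = 40 |

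With one group, two of the three planned effects cannot be tested. Time remains, as F(2, 42). With two groups, the interaction is F(2, 40).

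**Step 3: UAQ.** An independent-samples t-test needs two samples. If everyone is an SBS user there is one, and the test is undefined. The planned item means and SDs are unaffected.

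**Step 4: illustrative detectable effects.** These come from the noncentral t at two-sided 0.05 and 80% power, in SDs of the change score. The noncentrality is d√n for a change in one group of n (n − 1 df), and d√(n/2) for two groups of n each (2n − 2 df). Solving for d:

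| Reading of 22 | df | d | Noncentrality |
|---|---|---|---|
| One group of 22 | 21 | 0.63 | 0.626 × √22 = 2.94 |
| 11 per arm (assumed) | 20 | 1.26 | 1.256 × √5.5 = 2.95 |
| SBS arm is 22, plus 22 controls (assumed) | 42 | 0.86 | 0.865 × √11 = 2.87 |

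At 11 per arm, power is about 20% for a between-group difference of 0.5 SD and 43% for 0.8 SD. These are single t-test contrasts, whereas the planned interaction is a 2-df F test. They show only how far the meaning of 22 depends on which section is right.

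**The case against.** **The time effect is planned and can be run.** This stands. A reader might infer that the primary analysis cannot be run at all, but the SAP lists time as one of its three effects and one group is enough to test it. What fails is the group comparison and the conclusion drawn from the interaction.

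**A control arm may exist.** This also stands. A reader might infer that the trial is single-arm and that no comparator was ever enrolled. The documents do not settle that. The Objective's intervention-group label suggests another group, and the SAP refers to an assigned intervention and repeatedly to a paper-based regimen. The 22 might even be the SBS arm alone. Yet this does not remove the conflict: if there is a second arm, the Study Design's statements about all participants are wrong as written.

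**Some possible harms are not shown.** A reader might add that regression to the mean would be credited to the SBS. Nothing in the documents says participants are selected for low LOS, so that is not supported. Replacement of the analysis after the data are seen is likewise a risk, not something the documents show.

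**Detectable effects do not bear on a structural mismatch.** Fair; they are illustrative and the point does not depend on them.

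**Conclusion.** The point holds in this form: the Objective and Study Design, including the outcome table, conflict with the Statistical Analysis Plan on whether there is a comparator. Under the design as described, the group effect, the time by group interaction and the UAQ t-test cannot be estimated. Only the time effect remains, with 2 and 42 df if all 22 are complete, and it cannot separate the SBS from practice, exercise in general or natural change.

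The structural result rests only on the Study Design's statements that every participant is trained on, uses and rates the SBS. It needs no assumption about effect size. The detectable effects (0.63, 1.26 and 0.86 SD of the change score) do rest on assumptions: a two-sided test, 80% power and, for the last two, assumed arm sizes.

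The documents do not support going further and declaring either section the wrong one. The conflict must be resolved before analysis, because it decides whether the trial can make a comparative claim.

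**What to change.** State whether a paper-based arm is enrolled, then change the text to match, before any analysis.

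**If the trial has one arm**, revise the Statistical Analysis Plan:

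- Delete the group factor, the interaction, the UAQ t-test and all references to a paper-based regimen.
- Analyse each LOS direction with a one-way repeated-measures analysis over baseline, post and retention, and report changes from baseline with 95% confidence intervals. Naming week 6 as the main contrast is optional; the conflict can be resolved without ranking the time points.
- Summarise the UAQ descriptively, as already planned.
- Replace the language of efficacy and unique impact with change over time without a concurrent control.

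**If a paper-based arm is enrolled**, amend the Objective, the Study Design and the outcome table to state:

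- that arm and its regimen, and that only one arm uses the SBS;
- how participants are assigned;
- whether 22 is the total or the SBS arm, and the number in each arm;
- what the control arm rates on the UAQ, since several items concern the wearable system itself.

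**Cost.** The first route is a rewording of the SAP; the second is a protocol amendment. Neither adds participants or procedures to the trial as it is actually run. The downside of the one-arm version is that it gives up a comparative claim, which a one-group design could not support.

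### If a randomised two-group comparison is kept, the three-visit group main effect on LOS should not count as efficacy evidence, and a baseline-adjusted week-6 difference should be the primary estimate

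*Combined protocol and SAP*

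**What the plan says.** The Statistical Analysis Plan section introduces one repeated-measures ANOVA for LOS as its means of assessing efficacy. The factors are "time (baseline, post, retention) as a within-subject factor and group (intervention vs. control) as a between-subjects factor". The three visits are "baseline (Week 1, prior to intervention), post-intervention (Week 6), and retention (Week 10, one month after the intervention ends", so the first level of the time factor is measured before any treatment. No baseline covariate is specified. Nor does the section name a primary visit for LOS, or an effect estimate with a confidence interval.

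Three effects are tested: "Main effects of time and group, as well as the interaction effect". They "will be evaluated to determine whether balance performance improved differentially over time depending on the assigned intervention". Only one result is given an interpretation: "A significant interaction effect would suggest that the SBS system had a unique impact on improving LOS relative to the paper-based control regimen". Tests are run "with the significance level set at" 0.05.

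On sample size, the Objective section says only "Twenty-two subjects with idiopathic PD will be potentially recruited". The documents give no effect size, standard deviation, between-visit correlation, power, allocation ratio or dropout. The SAP speaks of an assigned intervention, but randomisation is never mentioned. The Study Design section has every participant exercising with the Smarter Balance System (SBS), which conflicts with the SAP's paper-based control group.

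**The concern.** Treatment cannot have changed a pre-treatment value. When that value is one of three outcome levels, the group main effect averages a visit with no treatment effect together with two visits that may have one. It therefore understates the benefit. It also takes in any baseline difference between the groups, which can be large by chance with about 11 people per group.

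The interaction does not have this fault. Its limits are different: it compares unadjusted change, spends two degrees of freedom, and when significant does not say at which visit or in which direction the groups differ. At stake is whether a small trial ends with a dated, interpretable treatment difference, or with an omnibus p-value beside a main effect that is easily misread.

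**Working it through.** **Inputs.** From the documents: N = 22, alpha 0.05, three visits, no baseline covariate. Assumed: n = 11 per group, 22 completers, equal variances, the same correlation rho between any two visits (compound symmetry), and two-sided tests. Effects are in SD units, d1 at week 6 and d2 at retention. Results are per LOS direction, with no multiplicity adjustment. The plan has no power figure to reproduce.

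**Dilution.** With no true baseline difference, the main effect estimates (0 + d1 + d2)/3. For a sustained effect d this is 2d/3. If half the benefit is retained, it is (0 + 1 + 0.5)/3 = 0.5 of the week-6 effect.

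**Chance imbalance.** The baseline difference has standard error sqrt(2/11) = 0.43 SD. Under randomisation a gap above 0.5 SD in either direction occurs about 24% of the time. Given a baseline gap b and no treatment effect, the expected main-effect difference is b(1 + 2rho)/3. For b = 0.5 SD and rho = 0.5 this is 0.33 SD.

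**Power.** Noncentrality (ncp), with m the mean of 0, d1 and d2:

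- Group main effect, F(1,20): m² / {[(1 + 2rho)/3](2/n)}
- Interaction, F(2,40): (n/2) × [sum of squared deviations of 0, d1, d2 from m] / (1 − rho)
- Week-6 ANCOVA, F(1,19): d1² / [(1 − rho²)(2/n)], divided by 19/18 for estimating the covariate slope
- ANCOVA on the mean of both follow-ups, F(1,19): [(d1 + d2)/2]² / {[(1 − rho)(1 + 2rho)/2](2/n)}, divided by 19/18

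For a sustained 1 SD effect at rho = 0.5:

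- Main effect: 0.444/(0.667 × 0.182) = 3.67, power 45%
- Interaction: 5.5 × 0.667/0.5 = 7.33, power 64%
- Week-6 ANCOVA: [1/(0.75 × 0.182)]/1.056 = 6.95, power 71%
- Adjusted follow-up mean: [1/(0.5 × 0.182)]/1.056 = 10.42, power 86%

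Simulation with 8,000 runs gave 44%, 64%, 71% and 87%.

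| Scenario (d1, d2) | rho | Interaction | Week-6 ANCOVA |
|---|---|---|---|
| 1, 1 | 0.3 | 49% | 62% |
| 1, 1 | 0.5 | 64% | 71% |
| 1, 1 | 0.7 | 86% | 86% |
| 1, 1 | 0.8 | 97% | 95% |
| 1, 0.5 (fades) | 0.5 | 51% | 71% |
| 0.5, 1 (grows) | 0.5 | 51% | 24% |

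Before the covariate cost, the ratio of the week-6 ANCOVA ncp to the interaction ncp for a sustained effect is 3/[2(1 + rho)], which equals 1 at rho = 0.5. The 7-point gain there comes from testing one contrast instead of two, net of the covariate cost. Against an unadjusted week-6 change score (61% at rho = 0.5), adjustment itself gains about 10 points.

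**Cost.** Error degrees of freedom fall from 20 to 19 (critical t 2.086 to 2.093). Variance rises by 19/18 = 1.056, or 5.6%.

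**Non-random groups.** Take a true, stable baseline gap of 0.5 SD and no treatment effect. Baseline adjustment leaves a bias of 0.5(1 − rho), which is 0.25 SD at rho = 0.5. In simulation the adjusted follow-up mean rejects 17%, 11%, 8.5% and 5.5% of the time at rho = 0.3, 0.5, 0.7 and 0.9. The interaction stays near 5%. The three-visit main effect rejects 34%, 29%, 24% and 21%.

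**The case against.** The strongest defence is that the SAP does not rest its efficacy claim on the main effect. It asks whether balance "improved differentially over time depending on the assigned intervention", which is an interaction question, and it interprets only the interaction. That stands. A reader might infer that the planned efficacy test is itself diluted or invalid; the documents do not support that. What remains is that the main effect is listed among the tests for assessing efficacy, and nothing says that it must not be read that way.

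A reader might also infer that baseline adjustment is free and always more powerful. Neither is so. It costs a degree of freedom. The week-6 comparison gains nothing at rho = 0.7, falls slightly behind at 0.8, and loses heavily if the effect grows by retention. The 87% figure belongs to the adjusted follow-up mean, which is not the primary recommended here. Nor is that mean a safe substitute: for a 0.8 SD effect present only at week 6, at rho = 0.5, it has 23% power against 45% for the interaction and 52% for week-6 ANCOVA.

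Two further objections stand as conditions. ANCOVA needs random allocation, which the documents never state. And if the single-arm design in the Study Design section is the true one, there is no group term, baseline as a level of time is the natural model, and this point falls away.

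**Conclusion.** The point holds in a limited, conditional form. If two groups are compared, the three-visit group main effect carries at most two thirds of a sustained effect, mixes in baseline imbalance, and should not serve as efficacy evidence. Under randomisation the imbalance adds noise, not false positives: simulated rejection with no effect was about 5%. A claim of inflated type I error would therefore need non-random groups.

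The interaction is a legitimate test that yields no dated or directional estimate. Compared with it, week-6 ANCOVA ranges from a 13-point gain to a 2-point loss for a sustained 1 SD effect over rho = 0.3 to 0.8. It gains about 20 points if half the benefit fades and loses 27 if the effect doubles by retention (both at rho = 0.5). The effect sizes, correlations and 11 v 11 split are all assumptions. The firmer reason to change is interpretability: one prespecified difference, at a named visit, with an interval.

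**What to change.** First reconcile the Objective and Study Design sections with the Statistical Analysis Plan on whether there is a control group, and state how participants are allocated.

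If the result is two groups with random allocation, then for each LOS direction:

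- Model week-6 and retention LOS with group, visit, group by visit, and baseline LOS in the same direction as a covariate.
- Make the adjusted week-6 group difference with 95% CI the primary estimate, and report the adjusted retention difference beside it.
- State that the group main effect from a model with baseline among the outcomes is not efficacy evidence.

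If the sponsor expects the effect to build up after week 6, it should weigh the choice of primary visit before data are seen, because the week-6 comparison is then the weaker test.

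If the groups are not randomised, keep the change-based interaction comparison, on the stated assumption that any baseline gap would have stayed constant without treatment.

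The cost is SAP wording, one error degree of freedom and about 5.6% variance inflation at N = 22. No new data are needed, since baseline LOS is already scheduled for everyone.

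### The SAP reads a significant time × group interaction as SBS improving LOS, but that 2-df omnibus F test carries no direction and no time point

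*Combined protocol and SAP*

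**What the plan says.** The Statistical Analysis Plan section specifies a repeated-measures ANOVA for range of LOS "with time (baseline, post, retention) as a within-subject factor" and "group (intervention vs. control) as a between-subjects factor". It will evaluate "Main effects of time and group, as well as the interaction effect", and gives the purpose as "to determine whether balance performance improved differentially over time depending on the assigned intervention". It then tells the reader how to take a positive result: "A significant interaction effect would suggest that the SBS system had a unique impact on improving LOS relative to the paper-based control regimen".

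The Study Design section says that "two primary outcome measures (range of LOS) will be used to evaluate static/dynamic balance performance", one for the anterior-posterior and one for the medial-lateral direction. It lists the baseline, Week 6 and one-month retention assessments without ranking them, and so does its outcome table. No section names a planned contrast, a post hoc comparison, a required direction, a primary time point, or a between-group estimate with a confidence interval. The SAP sets alpha at 0.05.

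**The concern.** The interpretation sentence attaches a signed conclusion (SBS improved LOS relative to control) to an unsigned test. The interaction F statistic is built from squared departures from parallel profiles. It can be significant because SBS improved more, because control improved more, because SBS fell back after Week 6, or because the groups parted only at Week 10. Only some of these are a benefit of SBS.

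This is the only statement in the documents that turns LOS data into a conclusion about efficacy. If it is followed literally, a trial in which SBS did worse could be reported as supporting it. Even if the analyst checks the direction, nothing fixed in advance says whether Week 6 or Week 10 should carry the conclusion, so that choice can be made after the data are seen.

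**Working it through.** The documents give no power, effect size, SD or correlation, so there is no planned figure to reproduce.

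**Inputs from the documents**
- Time: 3 levels. Group: 2 levels. Alpha: 0.05 (Statistical Analysis Plan).
- Total N: 22 (Objective: "Twenty-two subjects with idiopathic PD will be potentially recruited").

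**Assumptions not in the documents**
- 11 per arm, complete data, compound symmetry.
- Within-person correlation ρ from 0.5 to 0.8.
- Group difference d from 0.5 to 1.0 SD.

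**Degrees of freedom**
- Interaction: (3 − 1)(2 − 1) = 2.
- Error: (3 − 1)(22 − 2) = 40.
- Critical value at 0.05: F(2, 40) = 3.23.

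**Noncentrality**

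Let δ_t be the SBS-minus-control difference at time t in SD units, and δ̄ its mean over the three times. Then λ = (n/2) × Σ(δ_t − δ̄)² / (1 − ρ), with n = 11.

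- SBS better at both follow-ups, δ = (0, d, d): δ̄ = 2d/3, so Σ = d²(4/9 + 1/9 + 1/9) = 2d²/3.
- SBS worse at both, δ = (0, −d, −d): every deviation changes sign, the squares do not, so Σ = 2d²/3.
- Loss at Week 10 only, δ = (0, 0, −d): δ̄ = −d/3, so Σ = d²(1/9 + 1/9 + 4/9) = 2d²/3.
- Gain at Week 10 only, δ = (0, 0, d): again 2d²/3.

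For d = 1 and ρ = 0.5, λ = 5.5 × (2/3) / 0.5 = 7.33. For ρ = 0.7, λ = 5.5 × (2/3) / 0.3 = 12.22.

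**Probability of a significant interaction (noncentral F), the same for all four patterns**

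| ρ | d = 0.5 | d = 0.8 | d = 1.0 |
|---|---|---|---|
| 0.5 | 19.7% | 44.7% | 64.2% |
| 0.7 | 30.6% | 67.2% | 86.3% |
| 0.8 | 43.8% | 84.8% | 96.6% |

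Simulation agrees: with ρ = 0.7 and d = 0.8 (100,000 trials per pattern), the interaction was significant in 67% of trials for SBS better at both visits, SBS worse at both, and a Week 10 gain only.

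**Comparison with a signed contrast**

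The illustration is a between-group comparison of change from baseline to Week 6, two-sided 0.05, counted as benefit only if it favours SBS (ρ = 0.7, 11 per arm).

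| True state | Interaction significant | Signed Week 6 contrast favours SBS |
|---|---|---|
| SBS 0.8 SD worse at both visits | 67% | 0.0% |
| No difference | 5% | 2.5% |
| SBS 0.8 SD better at both visits | 67% | 63.5% |

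**Time point**

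With a true Week 10-only difference of 0.8 SD (ρ = 0.7), 93% of significant interactions came with a non-significant Week 6 contrast. The F test alone does not tell the reader that the signal lies at Week 10.

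**The case against.** The strongest reply is that the sentence says only that the result would suggest an impact. It is not a formal success rule, and any competent analyst would look at the means. That is largely right where SBS is worse throughout. In a simulation of SBS 1 SD worse at both visits (ρ = 0.5), only 0.2% of trials were significant without SBS also being numerically worse on change at both follow-ups. A reader might infer from the table that the trial would report harm as benefit 64% of the time. The documents do not support that: the figure is the chance that the stated condition is met, and the means would nearly always contradict the claim.

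Inspection helps less when the difference is at Week 10 only. With a true Week 10 gain of 0.8 SD (ρ = 0.7), 50% of significant interactions had SBS numerically worse on Week 6 change. By symmetry, a Week 10 loss would leave SBS numerically ahead at Week 6 about half the time, and the plan does not say which visit governs.

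Three further inferences are tempting and should not be drawn.
- **That a retention difference is not efficacy.** Retention is within the primary outcome's stated time frame. A gain seen only at Week 10 would be a real between-group difference. The gap is that no time point is named.
- **That a single Week 6 test would be more powerful.** This depends on the assumed profile. At ρ = 0.5, for effects of 1 then 0.5 SD, the omnibus test has 51% power and a Week 6 ANCOVA 71%. For 0.5 then 1 SD, the figures are 51% and 24%.
- **That the main effect of time is misread in the same way.** The SAP attaches no conclusion of improvement to that effect.

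**Conclusion.** The point holds as a fault in the interpretation rule. The SAP draws a directional conclusion from a test that cannot supply one, and nothing elsewhere in the documents repairs it. That SBS better and SBS worse by the same amount are equally likely to give significance follows from the squared form of the statistic. With normally distributed errors it does not depend on the SD, the correlation or the allocation. The percentages (64% at ρ = 0.5 and 86% at ρ = 0.7 for 1 SD) do rest on 11 per arm, complete data and the assumed correlation. The equal figure for a Week 10-only loss also needs compound symmetry. A sphericity correction would lower the effective degrees of freedom but would not give the test a direction.

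One prior question limits the point. The Study Design section has every participant using the SBS and describes no control arm, whereas the SAP compares SBS with a paper-based control. The between-group analysis can be run only if these two sections are reconciled.

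**What to change.** - Delete the sentence that equates a significant interaction with improvement.
- For each LOS direction, pre-specify signed between-group contrasts of baseline-adjusted LOS at Week 6 and at Week 10. Report each estimate with its 95% confidence interval.
- State in advance which time point is primary. If both are, apply a multiplicity adjustment such as Holm and base the claim on the adjusted result.
- Claim SBS benefit only where the interval excludes zero in SBS's favour. Keep the omnibus interaction as supportive.
- Reconcile the Study Design and SAP sections on whether a control arm exists, since these contrasts depend on it.

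The cost is SAP wording and slightly more analysis. Naming one primary time point makes the other secondary. Testing Week 10 only after a significant Week 6 result would usually block a formal claim for a delayed benefit, so that ordering is a trade-off for the sponsor to decide. Keeping both time points primary carries a modest multiplicity penalty.
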